The EHR will be queried 4 times over a 1 year period. At time of each query 1/4 of the target sample will be identified and randomized, and have the assigned interventions initiated. Each group will be followed for 12 months for the primary outcome: completion of any CRC screening test (guaiac fecal occult blood test, FIT, sigmoidoscopy, or colonoscopy), measured by evidence of screening documented within the EHR. Thus, the total recruitment period will last 12 months, and the duration through completion of 6 month follow up of all patients will be 24 months. Measurements will include demographic information (race, ethnicity, sex, and age), number and location of health center visits, primary provider, and comorbid medical conditions. In secondary analyses, we will determine whether screening rates vary across these characteristics, and also assess whether for significant interactions between characteristics and intervention effects.

Analytic approach and sample size, Aim 1. We estimated the sample size for 5 comparisons (usual care vs. inreach, usual care vs. outreach, usual care vs. inreach + outreach, inreach + outreach vs. outreach alone, and inreach + outreach vs. inreach alone), assuming $\alpha = 0.01$ across all groups and power ≥ 0.8 . For these assessments, we assumed the following rates of screening on follow up among individuals not up to date at baseline: 10% for usual care, 25% for inreach, 25% for outreach, 45% for inreach + outreach combined. The 10% rate for usual care and 25% estimate for outreach were conservative assumptions based on our previously cited work (30). The 25% rate for inreach was a conservative estimate based on observations that inreach interventions such as patient navigation have boosted screening completion (among patients referred for colonoscopy) by 41 to 78%. Finally, the 45% rate for both interventions combined was considered the minimal clinically significant difference that would justify implementing two different interventions for increasing screening. Under these assumptions, we computed need for a sample size of $n=648$ patients ($n=162$ for each group) to have sufficient power for all primary comparisons of interest.

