The primary outcome is completion of any CRC screening test (guaiac fecal occult blood test, FIT, sigmoidoscopy, or colonoscopy) within 12 months of randomization. The analytic approach taken will depend on whether or not an interaction exists between the outreach and inreach strategies on screening completion. If no interaction is present, screening rates for inreach vs. usual care and outreach vs. usual care will be compared using a Chi-square test of proportions, requiring $p < 0.01$ for statistical significance. If interaction is noted, we will compare screening rates with a Chi-square test of proportions for inreach without outreach vs. usual care, as well as inreach with outreach vs. usual care separately, using a $p < 0.025$ to indicate statistical significance. In both cases (interaction or no interaction), secondary comparisons will include inreach plus outreach vs. usual care, as well as inreach plus outreach vs. either strategy alone. We will conduct additional analyses treating screening completion as the dependent variable, and examine the relationship of group assignment, demographic characteristics, primary provider, and clinic visit frequency to this outcome. Factors associated with screening completion on univariate analyses will be considered as part of a logistic regression model examining factors independently associated with screening completion; in the case of interaction by group assignment a term for interaction will be included in our models. Additionally, interactions between other factors (e.g. gender, age, language preference, income, inreach strategy and frequency of clinic visits) will be considered.

Approach, Aim 2 Process Evaluation. Following the RE-AIM framework(41-43), a quasi-experimental process evaluation of intervention programs is proposed as part of the research protocol using validated measures developed in previous studies(44). This process evaluation is designed to examine the intervention’s acceptability, feasibility, and sustainability(45-47). Process measures include: intervention fidelity, recruitment and retention issues, dosage delivered and received, participant satisfaction, and *navigator* perceptions on areas for improvement in each one-on-one session. [name], [name], and [name] will lead trainings to ensure intervention fidelity and standardized intervention delivery and dosage.

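### The primary chi-square test is valid, but it leaves the four randomization waves and the collected baseline factors unused; a pre-specified adjusted test offers a small gain in power of uncertain size

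*Combined protocol and SAP*

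**What the plan says.** The design is described under 'Identification of candidate patients and recruitment'. The EHR is queried four times in a year: "At time of each query 1/4 of the target sample will be identified and randomized, and have the assigned interventions initiated". Wave is therefore part of how the trial randomizes. The same section lists what will be recorded: "Measurements will include demographic information (race, ethnicity, sex, and age), number and location of health center visits", together with primary provider and comorbidity.

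Under 'Analytic approach and sample size, Aim 1', the primary comparisons are chi-square tests in both branches. If there is no interaction between the strategies, the rates for inreach and for outreach, each against usual care, "will be compared using a Chi-square test of proportions", "requiring $p < 0.01$ for statistical significance". If interaction is noted, it tests inreach with and without outreach separately against usual care, "using a $p < 0.025$ to indicate statistical significance". Neither branch mentions wave or any covariate.

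Baseline factors are not ignored altogether. The plan has secondary analyses by patient characteristic, and an additional logistic model covering group assignment, demographics, provider and visit frequency. Covariates enter that model if they are associated with screening in univariate analyses. Wave is not named.

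**The concern.** An analysis that respects the randomization groups and adjusts for pre-randomization predictors usually estimates the treatment contrast more precisely. It also corrects chance imbalance in the factors that are fitted. Prior visits, age and clinic could plausibly predict who completes screening.

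The additional model does not fill this gap. It is not the primary test, it omits wave, and its covariates are picked from outcome data. It also admits primary provider, which may have many levels, and visit counts whose time window is not stated. Inreach acts at clinic visits, so visits counted after randomization would not be baseline information.

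At stake is a few points of power at most, and having a fixed covariate list in place of a data-driven one.

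**Working it through.** **1. Reproduce the stated sample size.** Inputs from the Aim 1 analytic section: 10% usual care, 25% for either single strategy, 45% combined, alpha 0.01, power at least 0.80. Sidedness is not stated; two-sided is assumed. The binding contrast is 10% vs 25%, with mean rate 0.175.

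n = [z(0.995)·√(2·0.175·0.825) + z(0.80)·√(0.10·0.90 + 0.25·0.75)]² / 0.15²
= [2.576·0.5374 + 0.842·0.5268]² / 0.0225 = 148.4, so 149 per arm.

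Continuity correction: (148.4/4)·[1 + √(1 + 4/(148.4·0.15))]² = 161.5, so **162 per arm**, exactly as stated. The 25% vs 45% contrast needs 142 with the correction.

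**2. Power of the planned test at 162 per arm, 10% vs 25%.**
- Uncorrected: Φ[(0.15 − 2.576·0.04222)/0.04139] = 84.1%.
- Continuity-corrected (0.15 reduced by 1/162): 80.2%.

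Both meet the target of 0.80.

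**3. Effect of adjustment, by formula.** Multiply both standard errors by √(1 − R²), where R² is the share of outcome variance explained by wave and covariates. The documents give no R², so this range is an assumption.

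| R² | 10% vs 25% | 25% vs 45% |
|---|---|---|
| 0 | 84.1% | 89.0% |
| 0.01 | 84.5% | 89.3% |
| 0.02 | 84.9% | 89.7% |
| 0.05 | 86.2% | 90.8% |
| 0.10 | 88.4% | 92.4% |

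**4. Wave alone.** Each wave has 648/4 = 162 patients, about 40 per arm, with about 4 usual-care events expected (40.5 × 0.10). If wave rates differ by up to 2 points either side, R² is about 0.001 to 0.003. In simulation (6,000 runs, balanced waves, log-odds shifts of −0.25, −0.10, 0.10 and 0.25), power was 85.0% for Pearson and 85.1% for a wave-stratified Cochran-Mantel-Haenszel (CMH) test. Across all simulated settings the gain was 0 to 0.7 points.

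**5. Wave plus covariates, by simulation.** 10% vs 25%, 162 per arm, two-sided alpha 0.01; covariate strength is assumed.
- Log odds ratio 0 per SD: about no change with a score test; a loss of about 1 point with a Wald test.
- 0.5 per SD: 84.9% to 86.6% with a score test (+1.7); +0.3 to +1.1 with a Wald test.
- 0.8 per SD: +2 to about +3.5, depending on the test.

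With no arm difference, rejection rates at nominal 1% were 0.75% to 1.1% for Pearson and about 0.9% to 1.2% for the adjusted score test with up to six covariates.

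**6. Models that are too large.**
- *Clinic.* The setting section lists nine primary care clinics. A model with intercept, arm, three wave terms, age, sex, visits and eight clinic terms has 16 parameters, against about 57 expected events (16 + 41). Simulated with nine equal clinics (assumed; 1,500 runs, Wald test), power fell from 86.5% to 85.1% with no prognostic factors. It rose only from 85.5% to 85.9% with one covariate at 0.5 per SD.
- *Provider.* Sixty uninformative indicators (number assumed; 2,000 runs, likelihood-ratio test) cut power from 85.2% to 82.7%. Type I error was about 2.3% at nominal 1%, against 1.4% for Pearson in the same runs.

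**7. The other readings of the primary comparison.**
- *Interaction branch:* alpha 0.025 gives about 91% for 10% vs 25%.
- *No-interaction branch, if it pools factorial margins:* usual-care side (10 + 25)/2 = 17.5%, intervention side (25 + 45)/2 = 35%, 324 per side. Power is about 99% at alpha 0.01, so adjustment has almost nothing to add.

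**The case against.** The strongest reply is that nothing here is broken. An unadjusted chi-square test is valid under randomization; its simulated type I error is close to nominal and the stated n meets its own target. That stands. A reader might infer that omitting wave makes the primary test wrong. It does not: if allocation is balanced within wave, the omission makes the test at most slightly conservative.

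A reader might also infer that adjustment gains power at no cost. The documents do not support that. They give no prognostic strength for any factor; a Wald test can lose about 1 point when the covariates predict nothing; and a full clinic or provider coding can cancel the gain or disturb type I error. A logistic odds ratio is also a conditional effect and does not by itself estimate the difference in screening rates.

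Nor is it right that 162 per arm leaves no spare power. The margin is thin only with the continuity correction (80.2%), or if usual care reaches the 12.1% that the Significance section reports from the earlier outreach trial. In that case power for 12.1% vs 25% is about 66%. Adjustment at the assumed 0.5 and 0.8 per SD would add about 2 and 5 points (66.9% to 69.1%; 66.7% to 71.5%), which helps but does not restore 80%.

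Finally, the no-interaction wording is ambiguous. Hypotheses 1a and 1b speak of each strategy with or without the other, which suggests pooled margins. On that reading the gain is negligible.

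What survives is narrower: the primary test leaves collected information unused, and the one adjusted model is additional and data-driven.

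**Conclusion.** The point holds as a low-priority efficiency improvement. The primary test is sound and the sample size reproduces. Wave stratification alone is worth well under 1 point of power. Adding a few pre-randomization covariates changes power at 10% vs 25% by about −1 to +3.5 points over an assumed log odds ratio of 0 to 0.8 per SD; the low end comes from a Wald test with uninformative covariates. These figures assume 162 vs 162, two-sided alpha 0.01, four balanced waves, and covariates measured before randomization. They do not carry over to pooled factorial margins, where power is already about 99%. A further benefit that does not depend on covariate strength is that a fixed list replaces selection by association with the outcome.

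**What to change.** Before outcomes are analysed, amend the Aim 1 analytic section as follows:

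- Make the primary test for each comparison a logistic model with arm, recruitment wave and a fixed covariate list: age, sex, and number of visits in the year before randomization. Include clinic only if it is grouped into a few levels. Do not include primary provider.
- Test the arm term with a score test, at the significance threshold the plan sets for that comparison.
- Report a standardized risk difference with its confidence interval, so that the effect stays on the scale of screening rates.
- Keep the unadjusted chi-square as a sensitivity analysis, and label the univariate-selected model exploratory.
- State the window over which visits are counted, and whether allocation is balanced within wave.

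The cost is a few sentences and a little more programming, with no extra patients. Age, sex, visits and location are already on the measurement list, though the visit window must be defined. The statistical downside is a possible loss of up to about 1 point of power if a Wald test is used and the covariates predict nothing; the score test largely avoids this.

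### If interaction is noted, the Aim 1 analysis names no test of FIT outreach alone against usual care, and the check that leads there is undefined

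*Combined protocol and SAP*

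**What the plan says.** All of this is in the section on analytic approach and sample size for Aim 1, except the hypotheses, which are in the Specific Aims.

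- **Selection rule.** "The analytic approach taken will depend on whether or not an interaction exists between the outreach and inreach strategies on screening completion". No test, effect scale or significance level is given for deciding this. The only interaction term described belongs to a later logistic model, and it enters only once interaction has been found.
- **No interaction.** "If no interaction is present, screening rates for inreach vs. usual care and outreach vs. usual care will be compared" by chi-square, with p below 0.01 required.
- **Interaction.** "If interaction is noted, we will compare screening rates with a Chi-square test of proportions for inreach without outreach vs. usual care", and also "inreach with outreach vs. usual care separately, using a $p < 0.025$ to indicate statistical significance".
- **Secondary, either way.** "In both cases (interaction or no interaction), secondary comparisons will include inreach plus outreach vs. usual care", plus the combined arm against each single strategy.
- **Further models.** Additional analyses will "examine the relationship of group assignment, demographic characteristics, primary provider, and clinic visit frequency to this outcome". They carry no decision rule.
- **Sizing.** "We estimated the sample size for 5 comparisons (usual care vs. inreach, usual care vs. outreach, usual care vs. inreach + outreach", plus the combined arm against each single strategy, at alpha 0.01 and power of at least 0.8. The section describes these as primary. The assumed rates are "10% for usual care, 25% for inreach, 25% for outreach, 45% for inreach + outreach combined", with 162 per group.
- **Hypotheses.** 1a and 1b claim superiority over usual care for inreach and for FIT outreach, each whether or not the other strategy is also given.

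**The concern.** The interaction branch names two tests against usual care, both involving inreach. The mirror test, outreach without inreach, is missing from the decision tests and from the secondary list. That conflicts with the sizing paragraph and with Hypothesis 1b.

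Two open points make the gap worse. The check that opens the branch is undefined, so its test, scale and alpha could be chosen after the results are known. The no-interaction contrasts are also open, because inreach against usual care can mean three things:

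- single arms (162 vs 162), as in the sizing;
- pooled margins (324 with inreach vs 324 without);
- Hypothesis 1a taken literally: everyone given inreach against the usual-care arm only (324 vs 162).

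The same holds for outreach. A smaller inconsistency is that, in the interaction branch, combined against usual care is both a 0.025 decision test and secondary.

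**Working it through.** **Inputs.** 162 per arm; rates 10/25/25/45%; thresholds 0.01 and 0.025, all from the Aim 1 section. Assumed here: two-sided tests, chi-square without continuity correction, and a Wald interaction check at 0.05 (range to 0.20), because the plan gives no sidedness and no alpha for the check.

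**1. The plan's own figure.** For 10% vs 25% at alpha 0.01 and power 0.8:

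n' = [2.576·√(2·0.175·0.825) + 0.842·√(0.09 + 0.1875)]² / 0.15² ≈ 148.4, so 149.

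With continuity correction, n = (n'/4)·[1 + √(1 + 4/(0.15·n'))]² ≈ 161.5, so 162. This matches. A single strategy against usual care drives the sample size; combined against a single strategy needs 142 and combined against usual care needs 43.

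**2. The scale matters.** At the planning rates:

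- Risk difference: 0.45 − 0.25 − 0.25 + 0.10 = +0.05 (SE √(0.7125/162) = 0.066).
- Ratio of odds ratios: (0.818 × 0.111) / 0.333² = 0.82 (log −0.201, SE 0.399).
- Ratio of risk ratios: (0.45 × 0.10) / 0.25² = 0.72 (log −0.329, SE 0.316).

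The sign changes with the scale. The asymptotic chance that the check fires is 11.7%, 7.9% and 18.0% at alpha 0.05, and 32.0%, 25.5% and 41.4% at 0.20.

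**3. Following the rule as written.** Simulation of 600,000 trials, check at 0.05, single arms:

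| | Risk difference | Logit | Log risk ratio |
|---|---|---|---|
| Interaction branch entered | 12% | 8% | 17% |
| Outreach alone vs usual care p<0.01, but no named test | 6% | 7% | 16% |
| Outreach alone vs usual care tested and significant | 79% | 78% | 69% |

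The last row is the 85% obtained if the comparison is always tested, minus the row above. With the check at 0.20, the middle row is about 22%, 22% and 39%.

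**4. Does the choice of scale change conclusions?** The risk-difference and logit checks choose different branches in about 17–18% of trials. The verdict on inreach differs in only about 2% (single arms).

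**5. The three readings, with inreach null (10/10/25/25%).** Inreach error under the whole rule, check at 0.05, is about 1–2% on single arms or on 324 vs 324 margins. The 324 vs 162 contrast compares an expected (10 + 25)/2 = 17.5% with 10%, and that difference is due to outreach alone. Overall rate 15%; SE under the null √(0.15·0.85·(1/324 + 1/162)) = 0.0344; SE under the alternative √(0.175·0.825/324 + 0.09/162) = 0.0316. The chance of rejecting in favour of inreach at 0.01 is Φ[(0.075 − 2.576·0.0344)/0.0316] ≈ 0.33; simulation gives 34%.

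**6. Threshold after the repair.** Three tests at 0.025 sum to 0.075. With all arms at 10%, the simulated chance that any of the three rejects is 6.2% at 0.025, 4.1% at 0.0167 and 2.6% at 0.01. Two tests at 0.025 give 4.4%.

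**The case against.** The best defence is that this is a drafting slip with an obvious intent. The sizing paragraph names outreach against usual care at 0.01 without making it conditional on anything. The secondary list need not be exhaustive. The regression on group assignment would probably estimate the effect. The only model with an interaction term is logistic, which suggests the logit scale, and there inreach power on single arms is 85% with or without the check.

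Much of this stands. A slip is the likeliest explanation. It still needs correcting, because no source named above supplies a decision test with a threshold inside that branch.

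Four stronger inferences are not supported:

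- **That outreach goes untested.** The combined arm against usual care covers the with-inreach half of Hypothesis 1b. Combined against inreach alone, which tests what outreach adds to inreach, is listed in both branches. Counting it at 0.01, some outreach test other than combined vs usual care is significant in 98%, 95% or 93% of trials (single arms). The 79/78/69% concerns outreach alone against usual care only.
- **That the two-stage rule badly inflates false positives.** On single arms or 324 vs 324 margins it does not. That reassurance fails only for the 324 vs 162 reading.
- **That 17–18% branch disagreement means as many changed conclusions.** The inreach verdict changes in about 2%.
- **That 162 per group is wrong.** It reproduces exactly.

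The double status of combined vs usual care is minor: at 45% vs 10% it is significant in essentially every trial.

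**Conclusion.** The concern holds as a conflict within the plan. Once interaction is noted, a hypothesised and sized comparison has no named test or threshold. At the planning rates and an assumed check alpha of 0.05, this lowers the chance of a tested and significant result for outreach alone by about 6 to 16 points, depending on the scale. The loss grows if the check uses a looser alpha. The undefined check alone would be missing detail; it matters here because it decides whether the test exists. The no-interaction contrasts need defining mainly to exclude the 324 vs 162 version, which would credit inreach with an outreach effect. It should be fixed before outcome data are seen. It does not call the randomisation or sample size into question. The percentages rest on the planning rates, two-sided tests and Wald checks; other interaction statistics would move them somewhat.

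**What to change.** 1. Add FIT outreach alone against usual care to the interaction branch, at the same threshold as inreach alone. If combined vs usual care stays a decision test there, use 0.01 as in the sizing, or at most 0.0167 (0.05/3). If it becomes secondary only, two tests at 0.025 can stay.
2. State that the no-interaction tests compare either single arms or 324 vs 324 margins, and rule out 324 vs 162 as a test of inreach or outreach.
3. Fix the test, scale and alpha of the interaction check before data are seen, and give combined vs usual care one status.

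The cost is a few sentences, with no added patients or data. The added test has 84% power at 0.01 (80% with continuity correction), 88% at 0.0167 and 91% at 0.025. Moving the interaction branch to 0.01 costs at most about 2 points of inreach power with the check at 0.05 (for example 87% to 85%, single arms, risk-difference check), and about 4 points with the check at 0.20.

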Despite potential opportunities to deliver screening for underserved populations through FQHCs, many challenges exist. Available strategies for screening promotion have undergone limited development and evaluation among low income predominantly Spanish-speaking FQHC Latino patients. Further, it is unclear which strategies are best for increasing screening, and whether implementing multiple approaches (e.g. inreach delivered at point of a medical visit vs. outreach not requiring an in-person visit) would be superior to taking one approach alone for optimizing screening rates. To begin to address these challenges, we have conducted pilot work that has 1) established an academic-community CRC partnership between UCSD, SDSU, and SYHC; 2) established that FQHCs are keenly interested in understanding the best and most practical strategies for screening promotion; 3) identified (through key informant interviews of providers, clinic leadership, experienced *promotoras* (community health workers), and screening experts) key themes our interventions must address; 4) adapted previous effective materials used for mailed FIT outreach and patient navigation-based in-reach for screening promotion. Now, utilizing this comprehensive partnership and pilot work, we propose the following specific aims:

Aim 1: Among 648 Latinos age 50-75 years served by the SYHC FQHC, not up-to-date with screening, compare impact of 4 strategies on screening completion via a randomized controlled trial. The strategies will include: a) a patient-navigation-based, in clinic, inreach strategy, b) a mailed FIT outreach strategy (FIT outreach), c) inreach + FIT outreach, and d) usual care (n=162 per group).

Hypothesis 1a: *The inreach strategy (with or without FIT outreach) will be significantly superior to usual care*

Hypothesis 1b: *FIT outreach (with or without the inreach strategy) will be significantly superior to usual care*

Hypothesis 1c: *FIT outreach + the inreach strategy will be significantly superior to either strategy alone compared to usual care.*

Aim 2: Conduct a process evaluation to examine the interventions' reach, effectiveness, acceptability, feasibility, and sustainability following the RE-AIM framework.

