The proposed research is innovative because it seeks to identify pragmatic interventions required to optimize CRC screening in a Latino underserved population, is highly feasible, and, will allow us to determine whether a combination of outreach and inreach interventions are superior to either strategy alone for increasing CRC screening. Further, the community-based partnership approach of linking our academic medical center/NCI-designated comprehensive cancer center (UCSD), a research university/Hispanic-serving institution (SDSU), and a large community health center (SYHC) may serve as a model for developing and implementing evidence-based interventions for traditionally underserved populations. Indeed, successful interventions will be demonstration of intervention effectiveness will support adoption by the SYHC, and disseminated through the local, regional and national CHC networks (e.g., Council of Community Clinics, California Primary Care Association, and the National Association for Community Health Centers). Overall, the research has potential to reduce cancer disparities among Latinos and other underserved populations served by FQHCs and beyond.

RESEARCH PLAN

SIGNIFICANCE

Colorectal cancer (CRC) is the 2nd leading cause of cancer death in the United States (US). CRC accounts for over 136,000 new cancer diagnoses, and over 50,000 deaths annually ⁽¹⁾.

Screening can reduce CRC incidence and mortality, but is underutilized, particularly among underserved populations. Randomized trials and observational studies have demonstrated that screening with fecal occult blood testing (including the guaiac fecal occult blood test (gFOBT) and the fecal immunochemical test (FIT)), sigmoidoscopy, and colonoscopy can reduce CRC incidence and mortality ⁽²⁻⁷⁾. As a result, the US Preventive Services Task Force has recommended screening for all individuals after age 50 years. However, according to the National Health Interview Survey (NHIS) the national screening rate is 59%, far below the 70% Health People 2020 target ⁽⁸⁾. Moreover, screening rates are particularly low among underserved populations, such as Native Americans, Asians, Latinos, individuals living in rural areas, individuals with lower education and/or socioeconomic position, and the under-/uninsured ⁽⁹⁾. For example, the screening rate among the uninsured is just 21% ^(10, 11).

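### The five comparisons sized as primary are not the ones tested: combined vs either strategy alone is only secondary, and once interaction is noted outreach alone has no decision test

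*Combined protocol and SAP*

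**What the plan says.** All references are to the combined protocol and SAP.

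- **Specific Aims.** For inreach, Hypothesis 1a claims: "The inreach strategy (with or without FIT outreach) will be significantly superior to usual care". The parallel claim for outreach, under Hypothesis 1b, reads: "FIT outreach (with or without the inreach strategy) will be significantly superior to usual care". A third, Hypothesis 1c, puts the combination above either strategy alone. The closing paragraph says that the trial "will allow us to determine whether a combination of outreach and inreach interventions are superior to either strategy alone for increasing CRC screening".
- **Analytic approach and sample size, Aim 1, first paragraph.** Five comparisons are sized at alpha 0.01 with power of at least 0.8: usual care against each of the three active arms, and "inreach + outreach vs. outreach alone, and inreach + outreach vs. inreach alone". Assumed screening rates are 10% (usual care), 25% (inreach), 25% (outreach) and 45% (both). The 45% was "considered the minimal clinically significant difference that would justify implementing two different interventions for increasing screening". The result, 162 per group and 648 in total, is said "to have sufficient power for all primary comparisons of interest".
- **Same section, second paragraph.** "The analytic approach taken will depend on whether or not an interaction exists between the outreach and inreach strategies on screening completion". With no interaction, inreach and outreach are each compared with usual care at p < 0.01. With interaction, the main tests are "inreach without outreach vs. usual care, as well as inreach with outreach vs. usual care separately", at p < 0.025. In both cases combined vs usual care and combined vs either single strategy are called secondary, with no threshold. The level and scale of the interaction test are not given.

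**The concern.** Two adjoining paragraphs disagree on which comparisons decide the trial.

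1. In the interaction branch, one of the two main inreach tests sets the combined arm against usual care. These arms differ by inreach and by outreach, so a positive result cannot be assigned to inreach. The next sentence lists the same comparison as secondary, so it has two ranks.
2. Combined vs outreach alone does isolate what inreach adds for patients who already get mailed FIT. It is sized as primary but analysed as secondary without a threshold, in both branches. The same holds for combined vs inreach alone.
3. Outreach alone vs usual care was sized and is part of Hypothesis 1b. Once interaction is noted, it is in neither the main nor the secondary list.

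The trial is meant to tell health centers whether to pay for one strategy or two. When the strategies interact, that question is hardest, and the main tests then do not address it. No rule says which result governs if a main test is positive and the secondary comparison is not.

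**Working it through.** **Inputs.** Rates of 10/25/25/45%, alpha 0.01, power 0.8 and 162 per arm come from the first paragraph of the Aim 1 analysis section. The thresholds of 0.01 and 0.025 come from the second. Two-sided testing is assumed because sidedness is not stated.

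**Step 1: reproduce the sample size.** Let d = p2 − p1, and let p be the mean of p1 and p2.

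n0 = [z(α/2)·√(2p(1−p)) + z(β)·√(p1(1−p1) + p2(1−p2))]² / d², then with continuity correction n = (n0/4)·[1 + √(1 + 4/(n0·d))]².

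For 10% vs 25%: n0 = [2.576·√0.28875 + 0.842·√0.2775]² / 0.0225 = 148.4, and n = 161.5, so **162 per arm**. This matches the plan exactly. The other sized comparisons need fewer: 142 (25% vs 45%) and 43 (10% vs 45%). The plan was therefore sized on single arms at 0.01 per comparison, and 5 × 0.01 = 0.05.

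**Step 2: set the sized comparisons against the interaction branch.**

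| Comparison | Sized as primary at 0.01 | Role once interaction is noted |
|---|---|---|
| Inreach vs usual care | yes | main, 0.025 |
| Outreach vs usual care | yes | not listed |
| Combined vs usual care | yes | main, 0.025, and also secondary |
| Combined vs outreach alone | yes | secondary, no threshold |
| Combined vs inreach alone | yes | secondary, no threshold |

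With no interaction, the last three are all secondary without a threshold.

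**Step 3: illustrate with assumed rates.** Suppose inreach works alone but adds nothing to outreach: 10/25/25/25% for usual care/inreach/outreach/both. These rates are an assumption, not the plan's. So is an interaction test at 5% or 10% on the logit or risk-difference scale. The simulation used 400,000 trials, 162 per arm and uncorrected two-sided chi-square tests.

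| Interaction test | Interaction noted | Both main inreach tests positive (all trials) | Combined vs outreach alone favours combined at 0.01, given interaction noted |
|---|---|---|---|
| logit, 5% | 78% | 71% | 0.05% |
| logit, 10% | 86% | 78% | 0.08% |
| risk difference, 5% | 66% | 59% | < 0.01% |
| risk difference, 10% | 77% | 69% | 0.02% |

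Where interaction is noted, combined vs usual care is significant in 91-92%.

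**Step 4: the plan's own rates (10/25/25/45%).** Interaction is noted in about 8-20% of trials over the same range of tests. Each such trial leaves outreach alone without a decision test.

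**Step 5: power if all five are tested at 0.01.** Power = Φ{[d − z(α/2)·√(2p(1−p)/162)] / √([p1(1−p1) + p2(1−p2)]/162)}.

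- 10% vs 25%: (0.15 − 2.576 × 0.0422)/0.0414 = 1.00, giving 84% (85% by simulation; 80% with continuity correction).
- 25% vs 45%: (0.20 − 2.576 × 0.0530)/0.0518 = 1.23, giving 89% (87% with continuity correction).
- 10% vs 45%: above 99.9%.

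**The case against.** The strongest reply is that the plan tests what it hypothesises. Hypothesis 1a speaks of inreach with or without outreach against usual care, and the interaction branch tests exactly those two versions. Aim 1 compares four strategies and never calls the design factorial. Whether the combination beats a single strategy is Hypothesis 1c, and that comparison is planned in both branches. In the 10/25/25/25% illustration it would almost never support an added benefit, so a careful reader would be warned.

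Much of this stands. The comparisons that isolate each strategy are planned, and combined vs usual care fits the wording of Hypothesis 1a. A reader might take the 59-78% as a false-positive rate. It is not: at those rates both arms truly beat usual care, and both rejections are correct.

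The reply does not settle the rank and threshold of Hypothesis 1c's comparisons, which the sizing paragraph calls primary. Nor does it supply a test of outreach alone. The logistic model with an interaction term could estimate that effect, but it is described as an additional analysis of factors associated with screening and carries no decision rule.

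**Conclusion.** The concern holds as a mismatch between the comparisons sized and those tested. It rests on the text alone: outreach alone vs usual care is unlisted once interaction is noted, combined vs usual care has two ranks, and Hypothesis 1c is tested without a threshold. The sample size itself is sound.

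The percentages depend on assumptions. The 66-86%, 59-78% and under 0.1% need the assumed 10/25/25/25% rates, and every figure for how often interaction is noted needs an assumed test level and scale. At the plan's own rates the interaction branch is the less common one (8-20%).

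A reader might also infer that the rule often credits an inert inreach strategy. The documents do not support that. With assumed rates of 10/10/25/25%, false credit is 4.6-9.6% only if any single positive test counts, a rule that the plan does not state. It is about 1% if both interaction-branch tests must be positive. A figure of 37-40% arises only if 324 inreach patients are pooled against the 162 in usual care, which does not fit a sample size built on single arms.

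**What to change.** - In both branches, make the five sized comparisons the primary tests, each at p < 0.01 on single arms of 162.
- Judge inreach by inreach alone vs usual care and by combined vs outreach alone. Judge outreach by outreach alone vs usual care and by combined vs inreach alone.
- Keep combined vs usual care as a primary test, but interpret it only as the effect of the package.
- Delete the p < 0.025 rule and the conflicting secondary label.
- Report the interaction test as a description of synergy, with its scale stated, so that it no longer selects the primary tests.
- Reword Hypotheses 1a and 1b to match: each strategy alone against usual care, and each strategy added to the other against that other strategy alone.

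This changes wording and ranking only and needs no patients or data. The cost is a stricter threshold for the two current interaction-branch tests. For inreach alone vs usual care at 10% vs 25%, power falls from about 91% at 0.025 to about 84% at 0.01. For combined vs usual care at 10% vs 45%, it stays above 99.9%.
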